## 12.2.15. Unscheduled Visits: To Occur as Needed

If additional visits are needed (e.g., for resolution of an adverse event), the following procedures and evaluations may be performed as needed:

- Vital sign measurements (sitting blood pressure, heart rate, respiratory rate, temperature)
- Complete physical examination, including weight
- Hematology, cystatin-C, serum chemistry and urinalysis
- Urine pregnancy test, if applicable. Positive results are to be confirmed with serum testing.
- Supine 12-Lead ECG (repeat three times consecutively within 30 minutes [must have an interval of at least 1-2 minutes between ECGs].
- Disease assessment (MRI, clinical status, corticosteroid use and overall disease assessment)
- Tesevatinib administration (if appropriate)
- AE assessment
- Concomitant medications
- Perform drug accountability, review patient diary, and collect old and dispense new study drug (if appropriate)

# **13.** STATISTICAL CONSIDERATIONS

All descriptive and inferential statistical analyses will be performed using the most recently released and available SAS statistical software or the most recently released and available version of R, unless otherwise noted.

Additional statistical details will be provided in a prospective statistical analysis plan (SAP).

# 13.1. General Design

This is an open-label phase 2, multicenter study of tesevatinib monotherapy in patients with recurrent glioblastoma.

# **13.2.** Sample Size Justification

This phase 2 trial is designed primarily to allow a preliminary assessment of the efficacy and safety of tesevatinib in the overall population of 40 patients with recurrent glioblastoma as well as to permit exploratory comparisons between predefined subgroups (by EGFRvIII mutation status and by EGFR gene amplification status). The target PFS-6 rate in the overall study population is 25%. PFS-6 rates seen in randomized studies with bevacizumab [Weathers 2015; Taal 2014; Galanis 2015] are of the order of 15-18%. Bevacizumab is registered in this indication.

With a sample size of 40 patients in the overall population, PFS-6 = 25% and median PFS-6 = 4.5 months, the trial has 95% power of having an estimated PFS-6 > 15%. Addressing uncertainty by the lower 90% confidence limit of the estimated PFS-6 – corresponding to a one-sided test on 5% significance level, the trial has 95% power to show a significant difference above 7% and 80% power to show a significant difference above 10%.

The power calculation is based on simulations in the Weibull distribution to describe the progression and survival times. The median PFS and the PFS-6 and the corresponding shape and scale parameters from the Weibull distribution are shown in Table 6 below.

	Median PFS (months)	6 month PFS	Weibull shape parameter	Weibull scale parameter
Overall population	4.5	25%	5.24	2.41

#### Table 6:Median PFS and PFS-6 Distributions

For the trial outcome, two subpopulations (A and B) are defined in Table 7.

Subpopulation	Description	Assumed proportion of subjects
А	Patients with an assumed beneficial mutation (EGFR gene amplified glioblastoma)	57%
В	Patients with an assumed beneficial mutation (EGFRvIII pos glioblastoma)	27%

#### Table 7: Assumptions for Distribution of EGFR Subpopulations

The trial is not stratified to include a specific proportion of patients with the EGFR gene mutations and is not powered to show significant differences for the secondary endpoints that estimate differences in PFS-6 for the two subgroups compared to patients without the EGFR gene mutations.

# 13.3. Interim Analysis

An interim analysis is included with the possibility to stop for futility. The stopping rule is based on an unacceptable PFS-6 rate of 5% and a desirable PFS-6 rate of 20% or more. The trial will continue after the interim analysis if more than 1 responder is seen in 21 patients giving a 72% probability of stopping if the PFS-6 rate is  $\leq$ 5%.

# **13.4.** Statistical Considerations

For categorical variables, the number and percent of each category within a parameter will be calculated for observed data only. For continuous variables, the mean, median, and standard deviation, as well as the minimum and maximum values, will be presented. The summary of time-to-event variables will include Kaplan-Meier methods as appropriate.

Statistical significance will be declared when the two-tailed p-value is found to be less than or equal to 0.05, unless otherwise noted. Missing data will not be imputed unless otherwise stated. All clinical data captured will be provided in data listings.

## **13.4.1.** Study Populations

Adult patients with recurrent glioblastoma with availability of paraffin-embedded tumor samples diagnostic of glioblastoma will be enrolled.

Two subgroups of patients are defined as having: EGFRvIIIpos and EGFR amplificationpos tumors.

Primary and secondary efficacy analyses will include all patients who were included in the study. The same analysis methods for the primary and secondary analyses will be applied to both the ITT population and the EGFRvIIIpos and EGFR gene amplificationpos population.

Safety analyses will include all patients who enrolled and received at least one dose of study treatment (the safety population).

All patients who take at least one dose of study drug will be evaluable for safety and efficacy assessments.

Patients who do not complete the study, for whatever reason, will have all available data (up until the time of termination related to the reason they were terminated) included in the analysis.

For statistical purposes completion of the study will be defined as six months after the last patient starts study treatment.

The plasma concentration analysis population will consist of all patients who receive at least one dose of tesevatinib, and who have at least one sample analyzed for plasma concentrations.

## 13.4.2. Patient Accountability, Demographics, and Baseline Characteristics

Patient disposition, demographic information and baseline characteristics will be tabulated for the overall population as well as by subgroups. Minimal data for screen failures, pertaining to why they failed to qualify to enroll will also be collected and listed.

#### **13.4.3.** Tesevatinib Exposure

The amount of tesevatinib administered by visit and overall (total dose) will be tabulated and presented by patient in data listings. The distribution of the number of cycles achieved per patient will also be summarized. In addition, delays and all other alterations in tesevatinib administration will be presented.

#### 13.4.4. Concomitant Medications

Concomitant medications will be coded using the current WHO Drug Dictionary and the data will be summarized and presented in tables and listings.

## 13.4.5. Plasma Concentrations

Plasma samples for tesevatinib concentration analysis will be drawn predose of tesevatinib on Day 15 of Cycle 1; and predose of tesevatinib on Day 1 of every subsequent cycle (up to cycle 6). Due to the sparse number of time points data are summarized using descriptive statistics by time points, systemic steroid treatment and subgroup.

These data, pooled with data from other studies, may be analyzed in a population PK analysis using nonlinear mixed effects modeling.

## 13.4.6. Efficacy/Activity

## **13.4.6.1.** Primary efficacy endpoint

## Progression-Free Survival at 6 months (PFS-6).

PFS is defined as the time between date of first dose and the date of first documented disease progression or death, whichever occurs first. The PFS-6 is defined as a patient being alive and progression free at 6 months (24 weeks). Disease progression will be determined based on investigator assessment with use of radiological assessments, clinical status, and corticosteroid

use. The specific criteria for disease progression is defined in Appendix 2. Patients without a date of disease progression or death will be analyzed as censored observations on the date of the last disease assessment; if no post-baseline disease assessment is available, PFS will be censored at the date of 1st dose.

The analysis of the primary endpoint and the estimation of PFS-6 is performed with a Cox model. Karnofsky performance status is included as a covariate. Study center is included as a random effect assumed to follow a gamma distribution. Thus, this is a shared Cox gamma frailty model. The model is used to estimate PFS-6 with 2-sided 95% and 90% confidence intervals.

Furthermore, Kaplan-Meier methodology will be used to estimate median PFS with 95% CI and the Kaplan-Meier curve will be constructed to provide a visual description of the PFS over time.

Descriptive statistics overall and for each parameter (radiological assessment, clinical status and corticosteroid dose) in the disease progression assessment are presented for the entire assessment period as well as for 3, 6 and 9-month time points.

#### 13.4.6.2. Secondary efficacy endpoints

The following subgroup PFS-6 endpoints:

- Investigator-assessed PFS-6 in the subgroup of patients with EGFRvIIIpos glioblastoma
- Investigator-assessed PFS-6 in the subgroup of patients with EGFR gene amplified glioblastoma

are evaluated using the same methodology as for the primary endpoint. The analysis is performed by including a subgroup factor as fixed effect in the model used to analyze the primary endpoint. PFS-6 with 95% confidence intervals are estimated for each subgroup as well as for the residual population.

Comparison of the efficacy between the subgroups and the residual group is performed by estimating the hazard ratio (HR) with 2-sided 95% and 80% confidence intervals and the p-value for the null hypothesis: HR=1.

Furthermore, Kaplan-Meier methodology will be used to estimate median PFS with 95% CI using Greenwood's formula and the Kaplan-Meier curves will be constructed to provide a visual description of the PFS for the subgroups over time.

Descriptive statistics overall and for each parameter in the disease progression assessment are presented for the entire assessment period as well as for 3, 6 and 9-month time points by subgroup.

The secondary endpoint:

• OS rate at 9 months (OS-9) and OS overall, in all patients and in those with EGFRvIIIpos and EGFR gene amplified glioblastoma

where OS is defined as the time between date of first dose of study drug and the date of death due to any cause. OS-9 is defined as the percentage of patients who are alive at 9 months.

Kadmon Corporation	Page 89 of 113	03 Apr 2019
	Confidential and	
	Proprietary	

Patients who are not reported as having died at the time of analysis will be censored at the date when they were last known to be alive; if no post-baseline data are available, OS will be censored at the date of first study drug. The analysis methods will be the same as for the PFS.

The secondary endpoints:

• ORR per RANO criteria, and DOR in all patients and in those with EGFRvIIIpos and EGFR gene amplified tumors

where ORR is defined as a CR or PR. Patients without a post-baseline disease assessment will be considered as non-responders. The analysis population for ORR will be all enrolled patients with measurable disease at baseline. An estimate of ORR and its 95% CI will be calculated using the Blyth-Still-Casella method for each treatment arm. CIs for the difference in ORRs between the subgroups will be determined using the normal approximation to the binomial distribution. In addition, ORR is analyzed with a generalized logistic regression analysis. Subgroup is included as fixed effect, KPS as a covariate and study center as random effect. The adjusted odds ratio for being a responder is estimated and the two-sided 95% confidence interval presented.

DOR is defined as the time from the initial response to disease progression or death among patients who have experienced a CR or PR during study. Patients who have not progressed or died at the time of analysis will be censored at the last disease assessment date. DOR will be estimated using Kaplan- Meier methodology. Comparisons between subgroups through use of the unstratified log-rank test will be made for descriptive purposes only.

- To evaluate the efficacy of tesevatinib as measured by PFS-6, OS-9, RANO ORR and DOR in the subgroups:
  - EGFRvIIIpos vs EGFRvIIIneg
  - EGFR amplificationpos vs EGFR amplificationneg

The statistics for these subgroup comparisons are described at each of the endpoints.

In addition, statistics for the change and percent change from baseline tumor measurements will be presented. These analyses will be done after each two cycles of therapy. Summary statistics will be produced for PFS and OS. The percentage of patients without disease progression after 3 and 6 months of dosing will also be presented separately by local (investigator) and potentially by central radiography results. Sites will provide copies of all MRI image sets for central retention in case central radiology review is required.

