#### 3.8.2.6 PFS-6, OS-9, ORR and DOR comparisons in the following subgroups

- EGFRvIIIpos vs EGFRvIIIneg
- EGFR amplificationpos vs EGFR amplificationneg

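### The only stated interval for the ORR difference between EGFR subgroups is a normal approximation, which under-covers for EGFRvIII at 11 v 29; the SAP names no method for the comparison

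*Protocol*

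**What the plan says.** Protocol 13.4.6.2 plans two comparisons of ORR between EGFR subgroups.

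- **Difference in rates:** "CIs for the difference in ORRs between the subgroups will be determined using the normal approximation to the binomial distribution". The confidence level is not given there; I take it as two-sided 95%.
- **Logistic regression:** "Subgroup is included as fixed effect, KPS as a covariate and study center as random effect". From it, "The adjusted odds ratio for being a responder is estimated and the two-sided 95% confidence interval presented".

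The same section limits the denominator: "The analysis population for ORR will be all enrolled patients with measurable disease at baseline". For the rate within a single group it names the Blyth-Still-Casella interval.

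The SAP is later and was written against Amendment 4. Its section 3.8.2.5 analyses ORR separately in Subpopulations A and B and in the mITT population, with Clopper-Pearson intervals from 3.1.4.2. Section 3.8.2.6 is headed "PFS-6, OS-9, ORR and DOR comparisons in the following subgroups" and contains only the two positive-versus-negative pairs. It names no interval, test or model. SAP 3.1.2 says in general terms that methods depart from the protocol where needed, but lists no individual change.

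**The concern.** The normal approximation estimates the variance of each rate from the observed rate. In a small group with few responses that estimate is often far too small, and it is zero when the group has no responder. The interval is then too short exactly when the data say least. If neither group has a responder, it collapses to the single point zero.

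The logistic model has a related weakness. When one subgroup has no responder, the maximum-likelihood odds ratio is zero or infinite; when neither has one, it is undefined.

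Both documents make the EGFR comparison of ORR a secondary objective, and protocol 7.2 says the sample size was also chosen to permit comparison by EGFR status. In a comparison without power the interval is the main result, so its width should be honest. The plan already avoids large-sample approximation for a single ORR (Blyth-Still-Casella in the protocol, Clopper-Pearson in the SAP). It uses one only for the difference, which rests on smaller groups.

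**Working it through.** **The plan's own figures.** The documents give no ORR, number of responders or coverage, so there is no ORR figure to reproduce. What can be checked is the power statement behind the sample size: "With a sample size of 40 patients in the overall population", 95% power above 7% and 80% above 10%. In 20,000 simulated trials of 40 Weibull times (shape 2.41, scale 5.24; Table 6 prints these two values under each other's headings), the lower limit of the two-sided 90% interval for PFS-6 exceeded 7% in 95.4% and 10% in 81.5%. This used limits on a log, log-log or logit scale. The sample size of 40 is therefore a sound input.

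**Inputs.**
- EGFRvIII-positive share 27% (Table 7): 0.27 × 40 = 10.8, so about 11 v 29.
- EGFR-amplified share 57% (Table 7): 0.57 × 40 = 22.8, so about 23 v 17.
- These sizes are upper bounds, because the protocol restricts ORR to patients with measurable disease.
- ORR 5-20% in each group: my assumption. It corresponds to 2 to 8 responders in 40.

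**Coverage.** The planned interval is d ± 1.96 × √[p₁(1−p₁)/n₁ + p₂(1−p₂)/n₂], where d = p₁ − p₂. Its exact coverage is the sum of Bin(x; n₁, π₁) × Bin(y; n₂, π₂) over all pairs (x, y) whose interval contains π₁ − π₂. The Newcombe interval, built from the two Wilson intervals, was enumerated in the same way. Coverage in per cent:

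| True ORR, positive v negative | Normal, 11 v 29 | Newcombe, 11 v 29 | Normal, 23 v 17 | Newcombe, 23 v 17 |
|---|---|---|---|---|
| 5 v 5 | 96.5 | 97.1 | 98.6 | 99.7 |
| 10 v 10 | 88.8 | 96.6 | 95.2 | 98.2 |
| 15 v 15 | 87.7 | 96.7 | 93.7 | 96.6 |
| 20 v 20 | 89.9 | 96.2 | 93.3 | 95.4 |
| 10 v 5 | 68.0 | 97.2 | 93.2 | 97.7 |
| 5 v 10 | 92.9 | 96.0 | 82.3 | 98.7 |
| 20 v 10 | 89.3 | 96.4 | 93.8 | 96.2 |
| Mean over 7 × 7 grid, 5-20% | 87.7 | 96.8 | 92.9 | 97.0 |
| Minimum over grid | 68.0 | 95.6 | 82.3 | 94.9 |

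The normal interval covers less than 90% in 65% of grid cells for EGFRvIII and in 8% for amplification.

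**Where the 68% comes from.** At 10% v 5% the true difference is +5 points. The positive group has no responder with probability 0.9¹¹ = 0.314. In that case the upper limit is highest with 1/29 in the other group: −0.034 + 1.96 × √(0.0345 × 0.9655/29) = +0.032. This is below +0.05, so every such trial misses. That accounts for 31.4 of the 32.0 points of non-coverage.

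**Why 5% v 5% looks adequate.** Neither group has a responder with probability 0.95⁴⁰ = 0.129. The interval is then 0 to 0, which contains the true difference of zero and counts as covering.

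**Non-estimable odds ratio.** The probability that at least one subgroup has no responder is 1 − [1−(1−π)^n₁] × [1−(1−π)^n₂]. At 10% for 11 v 29 this is 1 − (1−0.314)(1−0.047) = 0.346.

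| ORR in both groups | 11 v 29 | 23 v 17 |
|---|---|---|
| 5% | 67% | 60% |
| 10% | 35% | 24% |
| 15% | 17% | 8.5% |
| 20% | 9% | 3% |

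Adding KPS with an assumed distribution and no centre effect (2,000 simulations per case) barely changes these: 68, 37, 18 and 9% for EGFRvIII, and 60, 25, 8 and 3% for amplification.

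**Example.** With 0/11 v 2/29, d = −0.069. The normal interval is −0.069 ± 1.96 × √(0.069 × 0.931/29), or −16% to +2%. The Wilson limits are 0 to 0.259 and 0.019 to 0.220, so Newcombe runs from −0.069 − 0.151 = −22% to −0.069 + √(0.259² + 0.050²) = +19%.

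**The case against.** **The SAP may have dropped the protocol's method.** It replaces Blyth-Still-Casella with Clopper-Pearson and carries forward neither the difference interval nor the logistic model. A reader might infer either that the protocol's method certainly governs or that it was deliberately withdrawn. The documents settle neither: 3.1.2 is general and 3.8.2.6 is empty. What is firm is that no replacement is named and that the only method on paper performs poorly for EGFRvIII. The same sentence in the SAP would cure both.

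**The problem is not uniform.** A reader might infer that both EGFR comparisons under-cover across the board. The figures do not support that: for amplification, coverage is mostly 93-99% and 82% is an exception. The 68% for EGFRvIII is the worst cell of the grid, not a typical one.

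**The ORR is assumed.** This stands. A reader might take 2 to 8 responders as the plan's expectation, or conclude that the odds ratio will usually fail. Neither document supports the first, and the second is true only near the bottom of the assumed range.

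**Little rests on the comparison.** Protocol 13.2 calls the subgroup comparisons exploratory, the study is not powered for secondary endpoints, and no decision rule uses the ORR difference. Within-group rates already have exact intervals in the SAP. This limits the severity, but it does not justify an interval with the wrong coverage when a better one costs nothing.

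**The random centre term.** Nothing calculated here isolates harm from it, so I make no claim about it.

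**Conclusion.** The point holds in limited form. The SAP leaves the method for the ORR subgroup comparison blank. The protocol's normal-approximation interval, the only one stated, is not fit for the EGFRvIII comparison: about 88% average coverage against a nominal 95%, with a minimum of 68%. For amplification the loss is usually small, 1 to 3 points.

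Failure of the maximum-likelihood odds ratio is a serious prospect if the ORR is 5-10% (35-67% of trials for EGFRvIII, 24-60% for amplification). It is a lesser one at 15-20% (9-17% and 3-9%).

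These sizes rest on the Table 7 shares, all 40 patients being evaluable, a two-sided 95% level and an assumed ORR of 5-20%. Fewer evaluable patients would make the groups smaller still. Because the comparison is exploratory and unpowered, the severity is modest. The change is worth making because it is specific and nearly free.

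**What to change.** In SAP 3.8.2.6, and in protocol 13.4.6.2 so that the two agree, specify a two-sided 95% Newcombe or Miettinen-Nurminen interval for the ORR difference in both EGFR comparisons. Only Newcombe was calculated here.

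State whether the adjusted odds ratio is kept. If it is, fit it with Firth penalisation so that it stays finite when a subgroup has no responder, and say how centre is handled in that fit. KPS may stay: the protocol names performance status as prognostic, and including it barely affects estimability. A conditional exact odds ratio would not solve the problem, because it is still zero, infinite or undefined when a subgroup has no responder.

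The cost is a few sentences of SAP and protocol text and standard SAS options, with no new data. The intervals will be wider. By the same enumeration for 11 v 29, mean width rises from 38 to 47 percentage points at 10% v 10%, and from 52 to 53 at 20% v 20%. The increase is largest where responders are fewest (25 to 43 at 5% v 5%).

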## 13.4.6.3. Sensitivity analysis for primary and secondary PFS and OS endpoint analysis

As a sensitivity analysis for the primary and secondary PFS and OS analysis the estimation of PFS-X, medium PFS, OS-X and median OS is performed with parametric survival analysis models, the models are compared to the Cox model based on the AIC-value. For each model the PFS-X, medium PFS, OS-X and median OS confidence intervals are estimated.

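### The protocol's sensitivity analysis compares parametric survival models with the Cox model by AIC, but the two AICs come from different likelihoods and cannot be compared

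*Protocol*

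**What the plan says.** Protocol 13.4.6.1 estimates PFS-6 from a Cox regression with Karnofsky status as covariate and study center as a gamma-distributed random effect: "Thus, this is a shared Cox gamma frailty model". The OS analysis uses the same methods (13.4.6.2).

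Protocol 13.4.6.3 is the only section labelled as a sensitivity analysis for PFS and OS. Estimation of PFS-X, median PFS, "OS-X and median OS is performed with parametric survival analysis models", and "the models are compared to the Cox model based on the AIC-value". Confidence intervals are then given for every model. The section does not name the parametric families, the time unit, the likelihood behind the Cox AIC, or what follows from the comparison. Section 13.4.6.1 expresses the endpoint in both months and weeks, and section 13 allows either SAS or R.

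The SAP analyzes PFS-6 and OS-9 as proportions with Clopper-Pearson intervals (3.1.4.2, 3.8.1, 3.8.2.2) and PFS and OS by Kaplan-Meier (3.1.4.3, 3.1.4.4). Its only mention of a Cox model is in the sample-size text (3.1.3). It contains no parametric model, AIC or sensitivity analysis. Section 3.1.2 says only that methods were changed where necessary and does not list what was dropped.

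**The concern.** AIC differences are interpretable only when the competing likelihoods describe the same data. The Cox model leaves the baseline hazard unspecified, so its partial likelihood uses the order of the events and the risk sets but not the times themselves. A parametric model is scored on the density of the observed times, and that density carries the unit of measurement. Setting one AIC beside the other gives a number with no meaning as a measure of fit.

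At stake is how the sensitivity analysis would be read. A reported ranking of, say, Weibull above Cox would look like evidence about the shape of the hazard, when it reflects how time was stored or which likelihood the software prints.

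**Working it through.** **Inputs from the documents.** Protocol 13.2: "With a sample size of 40 patients in the overall population"; "PFS-6 = 25% and median PFS-6 = 4.5 months" (read as median PFS, as in Table 6); and the Table 6 row "Overall population 4.5 25% 5.24 2.41", with columns labelled shape and then scale for the last two figures.

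**Which Weibull.** Median = scale × (ln 2)^(1/shape) and S(6) = exp[−(6/scale)^shape].
- As labelled (shape 5.24, scale 2.41): median 2.25 months, S(6) essentially 0.
- Exchanged (shape 2.41, scale 5.24 months): median 4.50 months, S(6) = 25.0%.

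Only the exchanged values match the stated assumptions, so they are used below. The apparent label swap is a separate matter.

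**Reproducing the plan's power.** I used 4,000 simulated trials of 40 patients, no censoring, a Breslow estimate at 6 months from a Cox model without covariates, and a log-log lower 90% limit ("corresponding to a one-sided test on 5% significance level"). Estimate above 15%: 0.9535 (stated 95%). Lower limit above 7%: 0.9535 (stated 95%). Lower limit above 10%: 0.810 ("80% power to show a significant difference above 10"%). The match depends on the log-log limit; a log-scale limit gives 0.982 and 0.902 for the last two, and a linear limit gives 0.902 and 0.810. The simulation therefore represents the design. The plan states no AIC figure to reproduce.

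**Effect of the unit.** If time is multiplied by c, each event's density is divided by c, so a full-density AIC rises by 2 × events × ln(c). The partial likelihood does not change. For months to days, c = 30.4375 and ln(c) = 3.4157:
- 30 events: 2 × 30 × 3.4157 = 204.9
- 35 events: 239.1
- 40 events: 273.3

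The event counts are assumptions. Thirty corresponds to follow-up of exactly six months with 25% event-free and no dropout (40 × 0.75); 40 means that every patient has an event.

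Direct check on one simulated data set with 40 events: the Weibull AIC went from 173.82 in months to 447.08 in days (+273.25), while the Cox AIC stayed at 221.94. The preferred model changed on identical data.

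**Why the Cox figure says nothing about the times.** With 40 untied events, no censoring and no covariate effect, the partial likelihood is 1/40!. So −2 log L = 2 × ln(40!) = 2 × 110.32 = 220.6, whatever the event times are.

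**Repeated trials.** There were 300 simulated trials per scenario, with one Karnofsky-like covariate of no effect and no frailty. The second scenario assumes exponential censoring with mean 20 months.

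| Model, time unit | Mean AIC, 40 events | Beats Cox | Mean AIC, about 32 events | Beats Cox |
|---|---|---|---|---|
| Cox, any unit | 221.6 | – | 169.5 | – |
| Weibull, months | 171.8 | 100% | 141.8 | 99% |
| Weibull, weeks | 289.4 | 0% | 235.7 | 0% |
| Weibull, days | 445.0 | 0% | 360.1 | 0% |
| Weibull, log-time likelihood | 58.0 | 100% | 53.9 | 100% |

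In weeks or days no parametric model tried (Weibull, exponential, log-normal) beat Cox in any trial. The last row covers software that reports the likelihood of log(time): the unit then drops out, but the Weibull wins every time, so the comparison still does not discriminate.

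**The case against.** The strongest objection is that the step has no consequence and may already be obsolete. The later SAP, written to Amendment 4, contains no Cox fit to compare with. Section 13.4.6.3 says only that models are compared; it states no selection rule and reports every model's estimates with intervals, which is a usable robustness check without AIC. All of this stands, and it limits the reach of the point. It does not make the comparison valid. Nor does SAP 3.1.2 withdraw the step by name, while the SAP introduction says that it describes procedures as specified in the protocol.

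Two further limits stand:
- A reader might infer that the time unit alone always decides the ranking. That holds for the Weibull on full-density AIC in the scenarios above, but not generally. With about 32 events and time in months, the exponential (mean 171.6) lies close to Cox (169.5), and all three parametric models beat Cox in only 41% of trials. Under a log-time likelihood the unit has no role.
- A reader might infer that the trial's only robustness check is void. Section 13.4.6.1 also gives a Kaplan-Meier median and curve, and 13.4.6.2 foresees progression-free percentages by investigator and possibly by central radiography.

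**Conclusion.** The AIC comparison with Cox in Protocol 13.4.6.3 is invalid and should not be reported. The unit shift is exact for any full-density likelihood: about 205 to 273 AIC points from months to days for 30 to 40 events. The simulated preference rates rest on assumed event counts and censoring, on Table 6 with its labels exchanged, on a covariate with no effect and on no center frailty. They illustrate the defect and do not predict this trial's AICs. The invalidity follows from the likelihoods and does not depend on those assumptions.

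The consequence is limited. It would be tempting to conclude that the primary PFS-6 result hangs on the time unit. The documents do not support that: no estimate or decision is tied to an AIC winner, and the SAP's primary analysis is a binomial proportion. This is an error in one clause of a secondary, protocol-level analysis whose status under the SAP is left open.

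**What to change.** Either of two changes is enough.

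1. **Keep the analysis.** Delete the AIC comparison with Cox. Name the parametric candidates (for example exponential, Weibull, log-logistic, log-normal, generalized gamma), fit them to the same data in one stated time unit, and use AIC only among them. Compare the chosen model with the Cox or Kaplan-Meier result by overlaying the curves and tabulating PFS-6, OS-9 and the medians with their intervals. The SAP would need a short paragraph, since it has none on this now.
2. **Withdraw it.** State in SAP 3.1.2 that the analysis in Protocol 13.4.6.3 will not be done, and why. No labelled sensitivity analysis for PFS or OS would then remain, and the SAP should say so.

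The cost is about a sentence for withdrawal, or a short paragraph and trivial programming if the analysis is kept. Neither needs new data.
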